### 7.4. Analysis of incidences

The analyses will be performed on the ATP cohort.

The following analyses will be performed by study site and overall:

- Incidence proportion of RT-qPCR confirmed symptomatic dengue infection during the study period.
- Incidence proportion of virologically confirmed symptomatic dengue infection during the study period.
- Incidence proportion of probable symptomatic dengue infection during the study period.
- Incidence proportion of virologically confirmed or probable symptomatic dengue infection during the study period.
- The numerator will be the number of subjects with at least one specified event reported during the study period. The denominator will be the number of subjects in the ATP cohort.

95% CI accounting for clustering effect will be computed on all estimated incidence proportions. The method for estimating the CIs is described in Section 12.1.

- The proportion, with 95%CI, of subjects with Dengue Virus Ab.IgG positive result (ELISA) at Visit 1 will be tabulated by study site and age category.

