## 12. DATA DERIVATION RULE AND STATISTICAL METHODS

### 12.1. Methodology for computing CI

All confidence intervals (CIs) will be two-sided 95% CI.

This study will use cluster sampling (i.e. households within centers), inducing a potential clustering effect of the households and/or centers.

Individuals within a household are expected to have a more similar risk of infection compared to individuals from different households. For example, individuals living in the same household are more likely to share similar risk of being exposed to DENV infected mosquitoes. Similarly, subjects within a center may have a more similar risk of infection compared to individuals from different centers.

Therefore, CIs for proportions will account for clustering of observations. The 95% CIs will be based on generalized estimating equations (GEE) logistic regression model with robust variance estimate [Liang, 1986]:

- For an analysis by center, households will be considered as the clusters in the model.
- For an analysis on overall centers, the model with the highest estimated design effect (DE) among those using either households or centers as clusters will be used.
- SAS code:

```
PROC GENMOD DATA=xxx descending;
  CLASS cluster;
  MODEL event = / dist=bin link=logit;
  REPEATED subject= cluster / type=exch;
RUN;
```

Note that if the DE estimated from the selected GEE model is less than 1, then the classical logistic regression model will be used (GENMOD without cluster statement).

The design effect (DE), assessing the impact of clustered data on the variance of the estimated proportions (thus on the the precision of the estimated proportions), will be estimated as follows:

$$DE = \frac{\text{estimated variance accounting for the cluster sampling from GEE model}}{\text{variance estimated under the assumption of simple random sampling}}$$

If the proportion is 0% or 100%, or if all subjects used to compute the proportion are from the same cluster, then ICC, DE and 95%CI will not be estimated.

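### SAP 12.1 takes the CI from an exchangeable GEE, which with unequal clusters and correlated cases is not centred on the crude incidence proportion that SAP 7.4 defines

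*SAP*

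**What the plan says.** SAP 7.4 fixes the point estimate. For each outcome, "The numerator will be the number of subjects with at least one specified event reported during the study period", and "The denominator will be the number of subjects in the ATP cohort". That is the crude proportion, with every subject counted equally. SAP 7.4 then refers the reader to SAP 12.1 for the interval.

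SAP 12.1 states that "The 95% CIs will be based on generalized estimating equations (GEE) logistic regression model with robust variance estimate". The SAS code has an intercept only ("MODEL event = / dist=bin link=logit") and an exchangeable working correlation ("REPEATED subject= cluster / type=exch"). For the by-site results, "For an analysis by center, households will be considered as the clusters in the model". For the overall result, the clusters are households or centres, whichever gives the larger DE. There is a fallback: "Note that if the DE estimated from the selected GEE model is less than 1, then the classical logistic regression model will be used". No interval is estimated when the proportion is 0% or 100%.

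SAP 12.2 prints the incidence proportion and its limits to two decimals. Household size is not fixed: SAP 2.2.3 expects averages of 2 to 4 subjects per household, and SAP 7.1 tabulates the number enrolled per household. The SAP does not say that the GEE estimate can differ from the ratio in SAP 7.4, or which of the two is printed.

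**The concern.** An intercept-only GEE with exchangeable correlation does not weight subjects equally unless clusters are the same size or the estimated correlation is zero. With positive correlation, subjects in large households count for less. The interval is built around that re-weighted value on the logit scale, while SAP 7.4 defines the crude ratio.

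Two things follow. A reader of the primary table may see a proportion beside limits derived from a different sample value. Rows of the same table may also be centred differently: a site where two cases share a household takes the GEE branch, while a site with only isolated cases takes the fallback, which is centred on the crude value. SAP 10 reports that case numbers were low, so one household with two or three cases can decide which branch applies and how far the centre moves.

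**Working it through.** **The plan's own figures.** SAP 12.1 gives no numerical result. Protocol 10.2 does, and it reproduces:

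- DE = 1 + (3 − 1) × 0.4 = 1.8.
- Person-years = 1750 × (1.95 + 1.8525)/2 = 3327.
- Rate = 0.7 × 8 + 0.3 × 5 = 7.1 per 1000, about 23.6 cases.
- CI = 7.1 ± 1.96 × 1000 × √(23.6 × 1.8)/3327 = 3.3 to 10.9, as stated.

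These planning figures are not in dispute.

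**Formula.** With working correlation a, the estimating equation gives

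p(GEE) = Σ wᵢYᵢ / Σ wᵢnᵢ, with wᵢ = 1/[1 + (nᵢ − 1)a],

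where nᵢ is the size of cluster i and Yᵢ its number of cases. This equals ΣYᵢ/Σnᵢ for any data only if all nᵢ are equal or a = 0. At the protocol's planning value a = 0.4, the weight per subject is 1/1.4 = 0.714, 1/1.8 = 0.556 and 1/2.2 = 0.455 for households of 2, 3 and 4.

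**Assumptions.** The documents give neither the household-size distribution nor the number of cases. All household layouts and case counts below are illustrations.

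**One example in full.** Take 50 households of 2, 67 of 3 and 50 of 4 (501 subjects). There are 7 cases, split 3, 2 and 2 over three 4-person households. The fitted a is 0.6365.

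- Weights: 1/1.6365 = 0.6111, 1/2.2730 = 0.4400, 1/2.9095 = 0.3437.
- Numerator: 7 × 0.3437 = 2.406.
- Denominator: 100 × 0.6111 + 201 × 0.4400 + 200 × 0.3437 = 218.3.
- p(GEE) = 2.406/218.3 = 1.10%. Crude = 7/501 = 1.40%.

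**All examples** (95% CIs in %, robust variance by household; DE on the logit scale):

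| Layout | a | DE | Crude | TYPE=EXCH | TYPE=IND |
|---|---|---|---|---|---|
| Sizes 2–4, 7 cases, all in 4-person households | 0.64 | 2.40 | 1.40 | 1.10 (0.35–3.42) | 1.40 (0.45–4.30) |
| Sizes 2–4, 7 cases, two pairs in 2-person households | 0.26 | 1.70 | 1.40 | 1.56 (0.59–4.02) | 1.40 (0.55–3.48) |
| Sizes 1–8, 500 subjects, 7 cases, mainly in large households | 0.32 | 1.79 | 1.40 | 0.97 (0.36–2.59) | 1.40 (0.52–3.69) |
| Sizes 1–8, 348 subjects, 2 cases in a 6-person and 1 in a 4-person household | – | – | 0.86 | 0.68 (0.17–2.74) | 0.86 (0.20–3.56) |
| Sizes 1–8, 348 subjects, 3 cases in one 7-person household (extreme) | – | – | 0.86 | 0.41 (0.06–2.82) | 0.86 (0.12–5.75) |

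With 3 cases in about 350 subjects and a pair in a small household, the centre moves up instead, to as much as 1.04%.

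**Where nothing shifts.**

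- All households of size 4 (7 cases in 500): a = 0.18 and DE = 1.54, but crude and GEE are both 1.40% (0.56–3.46).
- Sizes 2–4 with no household holding two cases: a = −0.015 and DE = 0.97. The fallback applies and gives 1.40% (0.67–2.90).

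**Overall analysis with centres as clusters.** Assume 1 case in 350 in Mexico and 10 in 500 in the Philippines, with a = 0.00321.

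- Weights: 1/(1 + 349a) = 0.4716 and 1/(1 + 499a) = 0.3843.
- p(GEE) = (0.4716 + 3.843)/(165.1 + 192.2) = 1.21%. Crude = 11/850 = 1.29%.

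Here the re-weighting is by centre size.

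**How often.** These simulations assumed household sizes 1–8 with mean about 3, risk unrelated to size, and 350–850 subjects. The share of all data sets with a shift above 10% of the crude value was 0–1% at a true correlation of 0, 2–8% at 0.05, 6–11% at 0.1, 12–19% at 0.2 and 17–33% at 0.4.

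**The case against.** An exchangeable GEE with robust variance is a standard and valid method for clustered data, and the study is descriptive. The shift needs three things together: unequal clusters, a non-zero estimated correlation and a DE of at least 1. With few cases and none sharing a household, the DE falls just below 1 and the fallback returns the crude centre, so at a low-incidence site the mismatch may never appear. Protocol 10.2 calls its correlation of 0.4 conservative, so shift frequencies at that value are near the upper end. In the 7-case examples the shift was at most 0.43 points, against CI widths of about 2.2 to 3.4 points, and the crude value stayed inside every interval. The table templates are in a separate document, so a GEE estimate or footnote may be printed there. All of this stands, and it limits the point to a conditional one.

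A reader might go further and infer that the CI always belongs to a different quantity, that the rows estimate different population parameters, or that the primary estimate is biased. The documents do not support this. If risk is unrelated to household size, both estimators target the same population proportion and only their sample values differ. Bias for the subject-level proportion requires risk that depends on household size, and neither document says that it does.

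The objection does not remove the gap itself. SAP 7.4 defines one number, and the code in SAP 12.1 can centre its interval on another without any statement that it does so.

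**Conclusion.** The point holds in conditional form. When clusters are unequal, the estimated correlation is not zero and DE is at least 1, the CI in SAP 12.1 is centred on a re-weighted proportion instead of the SAP 7.4 ratio. The direction depends on which households hold the cases. In the illustrations the shift was 0.05 to 0.43 points on an assumed 1.40%. On 0.86% the centre ran from 0.68% to 1.04%, or 0.41% in the extreme case, where the upper limit is about half that of the interval around the crude value (2.82% against 5.75%). Shifts of this size show at two decimals.

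The size rests on assumed household layouts and case counts; the mechanism is algebra. Coverage is about the same either way, so it would be wrong to read this as an invalid interval. It is a mismatch between a printed estimate and its CI, and it should be corrected because the correction costs almost nothing.

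**What to change.** In SAP 12.1, replace TYPE=EXCH by TYPE=IND and keep the robust (empirical) variance. Leave the choice of cluster as specified: household by site, and household or centre overall. The intercept then back-transforms exactly to cases divided by ATP subjects in every branch, including the DE-below-1 fallback, and the interval still allows for clustering. The DE becomes a ratio of two variances of the same estimate. SAP 12.1 also refers to an intra-cluster correlation; if one is reported, take it from a separate exchangeable fit and label it so.

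The cost is one word of code and one or two sentences in the SAP, with no change to data or conduct. The downside is a possible small loss of efficiency. If the sponsor prefers to keep TYPE=EXCH, the minimum is to print the GEE estimate beside its CI and state how it is weighted.

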**12.2. Data presentation**

The following decimal description will be used for the analyses:

Display Table	Parameters	Number of decimal digits
Dengue cases	Incidence proportion, including LL & UL of CI	2
Dengue cases	Percentage	1
Demographic characteristics/ baseline characteristics	Percentage, mean, median, standard deviation, minimum, maximum, Q1, Q3	1

CI = confidence interval  
 LL = lower limit of the confidence interval  
 SD = standard deviation  
 UL = upper limit of the confidence interval  
 Q1/Q3 = 25th and 75th percentiles

**12.3. Handling missing data**

No data handling will be performed in case of missing data.

**12.4. Data derivation**

**12.4.1. Date derivation**

SAS date derived from a character date: in case day is missing, 15 is used. In case day and month are missing, 30 June is used.

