### **6.1. Suspected symptomatic dengue case**

Acute febrile illness measured as  $\geq 38.0^{\circ}\text{C}$  with a thermometer by any route or recent history of febrile illness (onset in the past 8 days) reported by the subject/the parent(s)/LAR(s)/ designate (if applicable) of the subject for at least two consecutive days (a duration of approximately 36-48 hours) and of less than 7 days duration, which may be accompanied by other dengue symptoms or signs and does not have a defined focus or an obvious reason unrelated to dengue (based on physician judgement).

Note: Besides fever, other dengue associated signs and symptoms include but are not limited to: upper respiratory tract symptoms like cough, nasal congestion, runny nose and dyspnoea, gastrointestinal symptoms and febrile convulsion in infants/older children and fatigue, headache, pain behind the eyes, abdominal pain, nausea, vomiting, muscle ache, joint ache, diffuse rash on the trunk, itching of skin (pruritis) in adults/adolescents.

A number of infectious and non-infectious diseases mimic dengue and severe dengue. Physicians should be careful not to rule out dengue diagnosis too quickly, when the differential diagnosis cannot be accurately made. Early symptoms of dengue may include gastrointestinal and upper respiratory symptoms and may be misdiagnosed as diarrhoeal diseases or other diseases with flu-like symptoms. The WHO handbook for clinical management of dengue provides a list of conditions that mimic the febrile phase and the critical phase of dengue infection.

A SDC presenting at the health care facility within 5 days following the onset of symptoms (i.e. day of symptoms onset and the next 4 days) will be defined as an 'early presenter'. A SDC presenting at the health care facility 6 days or more after the onset of symptoms will be defined as 'late presenter'. Both early and late presenters will have a scheduled visit at the study healthcare centre including blood sampling for laboratory diagnosis.

Seven consecutive calendar days without fever (body temperature  $\geq 38.0^{\circ}\text{C}$ ), in the absence of antipyretic medication, are required to separate two episodes of SDC.

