### 7.3. Characteristics of the suspected dengue cases

The analyses will be performed on the ATP cohort.

SDC will be listed with the following characteristics: study site, date of first visit for SDC, subject number, household number, dengue episode number, age at first symptom onset, gender, time interval between fever onset and first visit for SDC (in days), time interval between first symptoms onset and first visit for SDC (in days), early/late classification (based on interval between date of symptoms onset and date of first visit for SDC), date of blood sample, laboratory results at first visit for SDC, dengue classification (virologically confirmed, probable, other SDC), Dengue Virus Ab.IgG antibodies (ELISA) at Visit 1, hospitalization (Yes/No), at least 1 WHO 2009 warning signs (Yes/No), at least 1 WHO 2009 criteria for severe dengue (Yes/No) and most likely diagnosis (investigator opinion).

Distribution of suspected dengue cases type (early/late presenters) by month will be displayed graphically by study site and overall.

The following characteristics will be summarized for each category of dengue cases (Virologically, probable, other SDC):

- Temperature at first visit:  $<37.5$ ,  $\geq 37.5$ ,  $>38$ ,  $>38.5$ ,  $>39$ ,  $>39.5$ ,  $>40$
- Clinical symptoms at onset, from first and returned visits: frequency and proportion of cases with each symptom
- Final classification of the episode (hospitalisation (yes/no), at least one WHO 2009 warning signs (yes/no), at least one WHO 2009 criteria for severe dengue (yes/no), most likely diagnosis according to investigator opinion (dengue, chikungunya, influenza, malaria rotavirus or other enteric infection, other infection disease or non-infectious disease)).

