**12.4.3. Time interval**

Time interval between 2 visits is expressed in days. It is the number of days between the 2 visit dates. Therefore, the time interval is of 0 day if the 2 visit dates are the same.

Time interval expressed in years will be computed as follows: time interval expressed in days/365.25.

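### The SAP's partial-date rule (day 15, or 30 June) does not exempt symptom-onset and fever-onset dates, so a partial onset date would give a false onset-to-visit interval and an arbitrary early/late class

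*SAP*

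**What the plan says.** SAP 12.4.1 sets one rule for turning a partial character date into an analysis date: "in case day is missing, 15 is used. In case day and month are missing, 30 June is used". It names no variable to which the rule does not apply, does not cap the imputed date at the visit date, and asks for no plausibility check. The section before it, SAP 12.3, says "No data handling will be performed in case of missing data".

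SAP 7.3 uses onset dates in the listing of SDCs. For each case it lists "time interval between fever onset and first visit for SDC (in days"), "time interval between first symptoms onset and first visit for SDC (in days"), age at first symptom onset, and an "early/late classification (based on interval between date of symptoms onset and date of first visit for SDC"). It also graphs early and late presenters by month, for each site and overall.

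SAP 6.1 sets the scale of these variables. An early presenter is seen within 5 days, which the SAP explains as "i.e. day of symptoms onset and the next 4 days"; a late presenter is seen 6 days or more after onset. Where fever is reported rather than measured, the case definition requires a "recent history of febrile illness (onset in the past 8 days"). SAP 12.4.3 defines an interval as a plain difference ("It is the number of days between the 2 visit dates"), with no lower bound.

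**The concern.** Mid-month imputation does little harm when the quantity derived from the date runs over years. Here the quantity runs over days. The early/late cut-off lies at about 5 days and the reported-fever window is 8 days, while substituting the 15th can move an onset date by two weeks in either direction. The rule also ignores what is already known about an SDC: onset cannot fall after the first visit.

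The derived interval and class would then depend on the calendar day of the visit and not on the patient's history. At stake is the case-level description. SAP section 10 drops the incidence sub-analyses because few confirmed or probable cases were seen, so the SDC listing carries much of what will be reported about individual cases. A reader will use the onset-to-visit interval there to judge how informative a negative RT-qPCR is.

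**Working it through.** The plan gives no figure on this point, so there is none to reproduce. The check applies the SAP rule by enumeration.

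**Inputs from the SAP.** Imputed day 15, or 30 June (12.4.1). Interval = first-visit date minus onset date (7.3, with the convention of 12.4.3). Early = difference of 0 to 4 days; late = 6 days or more (6.1). A difference of exactly 5 is not clearly assigned, so late was taken as ≥5 and then as ≥6. Seasons: Mexico 1 July to 30 October, Philippines 1 May to 30 November (2.4).

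**Assumptions.** Onset or visit days are uniform; the true lag *k* is uniform over 0 to 8 days; the year (and, for the day-15 rule, the month) of onset is recorded correctly; a negative interval counts as not late.

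**Single cases, day missing, onset recorded as July.**
- Visit 6 July: 6 − 15 = −9 days.
- Visit 19 July: 19 − 15 = 4 days, early.
- Visit 21 July: 21 − 15 = 6 days, late.
- Visit 28 July: 28 − 15 = 13 days, late.

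All four results are the same whatever the true onset day in July.

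**Day missing, 30-day month.** With true onset day *d* = 1 to 30 and *k* = 0 to 8 there are 30 × 9 = 270 combinations, and the imputed interval is *d* + *k* − 15.
- Negative when *d* + *k* ≤ 14, which is 14 − *k* values of *d* for each *k*: 126 − 36 = 90, and 90/270 = 33.3%.
- Above 8 when *d* + *k* ≥ 24, which is 7 + *k* values: 63 + 36 = 99, and 99/270 = 36.7%.
- Between 0 and 8: 270 − 90 − 99 = 81, or 30.0%.
- Wrong class, late ≥5: 65 early cases become late and 50 late cases become not late; 115/270 = 42.6%.
- Wrong class, late ≥6: 75 + 39 = 114; 114/270 = 42.2%.

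**Day missing, actual calendar.** Every visit date in 2017 and 2018 with lags 0 to 8 gives 730 × 9 = 6,570 combinations. Negative: 2,160 (32.9%), as low as −14 days. Above 8: 2,466 (37.5%), up to 24 days. Wrong class: 42.8% (≥5) or 42.6% (≥6). With other lag ranges (0–7, 0–5, 2–3) and within each dengue season, 33–38% are negative, 33–38% exceed 8 days, and 42–46% of classes are wrong.

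**Day and month missing (30 June), lags 0 to 8.**

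| Visit dates | Negative | Above 8 days | Wrong class, late ≥5 | Wrong class, late ≥6 |
|---|---|---|---|---|
| Mexico season | 0% | 93.4% | 606/1,098 = 55.2% | 717/1,098 = 65.3% |
| Philippines season | 28.0% | 67.8% | 1,005/1,926 = 52.2% | 1,086/1,926 = 56.4% |
| Whole of 2017–2018 | 48.2% | 49.3% | 3,248/6,570 = 49.4% | 3,252/6,570 = 49.5% |

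**Could the month alone rescue the class?** If onset is bounded by the known month, the visit date and the 8-day window, the class is settled in only about 9–10% of combinations. In the other 90–91% it stays open.

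**The case against.** The strongest objection is that no affected date is shown. The documents do not say whether the eCRF accepts a partial onset date, or that one was recorded. The design makes them unlikely: contact is preferably weekly, a diary log records temperature and symptoms until the appointment (Protocol 7.5.1.11), and a physician can hardly apply the case definition without a near-exact onset. A missing day and month for an illness about a week old is hard to imagine. All of this stands. The percentages above are conditional on a partial date and are not an estimate of error in this study. An impossible interval would also be visible in the listing, which shows the first-visit date.

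Four stronger readings are tempting, and the documents do not support them.

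- *About 70% of imputed intervals are impossible.* Only the negative third is strictly impossible. The 8-day limit applies to reported fever, and the class uses first symptom onset, which may precede fever. Intervals above 8 days are inconsistent with the fever window and no more than that.
- *Under the 30 June rule almost every result is wrong.* That is close to true of the intervals, since over the whole calendar only 2.5% fall within 0 to 8 days. It is not true of the early/late class, where 49–65% are wrong.
- *The rule decides who is a probable case, or touches the primary result.* SAP 6.2.3 mentions late presenters only where RT-qPCR was not performed, and SAP section 7 lists RT-qPCR as available for both early and late presenters. RT-qPCR confirmation rests on the RNA result (12.4.5), and the incidence denominator is a count of subjects (7.4). None of these uses an onset date.
- *Sections 12.3 and 12.4.1 contradict each other.* They sit awkwardly, but one can be read as a general statement and the other as a specific rule for partial dates.

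What survives is narrower: the written rule, applied as written to a partial onset date, gives a wrong answer.

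**Conclusion.** The point holds as a minor fault in a stated rule. For an onset date without its day, about 33% of imputed intervals would be negative, about 37% would exceed 8 days and about 43% of early/late classes would be wrong. With the month also missing, about 49–65% of classes would be wrong. Even the remaining 30% or so of day-missing intervals that look plausible are set by the calendar day of the visit.

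These rates rest on uniform days and lags of 0 to 8 days; under the day-15 rule they move little with the lag range, the season or the cut-off at day 5. How often a partial onset date occurred is unknown and may be never.

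The reach is the SDC listing (both intervals, the early/late class, and age at symptom onset where the imputed date crosses a birthday) and the monthly early/late graph. No incidence result depends on it.

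**What to change.** Add one sentence to SAP 12.4.1: symptom-onset and fever-onset dates are not completed by the day-15 or 30 June rule; where the day cannot be recovered by the usual data query, the onset-to-first-visit interval is left missing and the early/late class is shown as 'unknown'. The rule can stay for other partial dates.

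The cost is one condition in the derivation program and a possible 'unknown' category in the listing and graph. Because the month alone rarely settles the class, most unresolved partial dates would land there, which reports honestly what is known. No false interval would then be created by imputation.

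Make no change to the probable-case definition in SAP 6.2.3. It repeats Protocol 5.2, and nothing here shows a need to alter it.
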